4.2.2 SECONDARY ENDPOINTS

Secondary outcomes will be obtained by chart abstraction after delivery. These include the following:

- Total cesarean section rate
- Cord blood gases
- Cases of SGA undetected prenatally.
- Birthweight/ birthweight percentile
- Incidence of category 2 or 3 tracings
- Distribution of CPR by EFW
- Rate of operative vaginal delivery
- NICU admission
- Apgar scores at 1 and 5 minute
- Composite neonatal outcome

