	pregnancies complicated by IUGR. The CPR may predict adverse outcomes in low risk pregnancies. In a prospective study, we will examine whether fetuses with an abnormal CPR at or near term are at increased risk for being delivered by cesarean
Objective	To assess whether women with appropriately grown fetuses in otherwise low risk pregnancies with an abnormal CPR are more likely to be delivered by cesarean section
Endpoints	
Primary outcome variable:	Cesarean for non-reassuring fetal heart tracings
Secondary outcome variables:	Total cesarean delivery rate Umbilical cord blood pH Unidentified small for gestational age births Birthweight percentile Prevalence of category 2 or 3 fetal heart tracings Distribution of CPR by EFW Rate of operative vaginal delivery NICU admission Apgar scores at 1 and 5 minutes Composite neonatal outcome
Population	Healthy women with low-risk pregnancies receiving care at study institutions
Number of Sites enrolling participants	8
Description of Study Agent	Prenatal ultrasound Doppler assessment of the umbilical and middle cerebral arteries
Study Duration	12 months
Participant Duration	Between 1 day and 6 weeks

SCHEMATIC OF STUDY DESIGN

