2 INTRODUCTION: BACKGROUND INFORMATION AND SCIENTIFIC RATIONALE

2.1 BACKGROUND

The CPR was first described in the 1980's. The CPR is calculated by dividing the Doppler indices of the middle cerebral artery (MCA) by the umbilical artery (UA). Most commonly, the pulsatility index (PI) is used to calculate the CPR. The CPR represents alterations in blood flow to the brain as a result of cerebrovascular dilation in response to hypoxia and increased placental resistance. The CPR has been best studied as a predictor of adverse pregnancy outcomes in fetus diagnosed with growth restriction. Newer studies have suggested the use of the CPR as an alternative approach for appropriately grown fetuses suffering from placental insufficiency who haven't reached their full growth potential but do not appear to be growth restricted (Morales-Rosello et al, Ultrasound Obstet Gynecol Jan 2015).

There is preliminary evidence that an abnormal CPR predicts adverse outcomes in otherwise low risk pregnancies. In a study by Prior et al. (Amer J Obstet Gyn February 2013) appropriately grown fetuses with an abnormal CPR (less than the 10th percentile) were 4 times more likely to be delivered by cesareansecondary to fetal distress in labor. A second study published by Morales-Roselló et al (Journal of Ultrasound in Obstetrics and Gynecology in

January of 2015) showed that appropriately grown fetuses with abnormal CPR were more likely to have lower cord blood gas pH levels.

The current standard of care is only to perform Doppler studies in growth restricted fetuses. Currently there is not data to support Doppler studies in the low risk obstetrical population. Our primary aim to investigate the value of assessing the CPR in fetuses that are at low risk for adverse outcomes.

While these limited data suggest that the CPR may be useful in predicting which women need cesarean and are at increased risk for abnormal fetal heart rate tracings and fetal acidosis, these data are only preliminary and further study is necessary.

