4 STUDY DESIGN AND ENDPOINTS

4.1 DESCRIPTION OF THE STUDY DESIGN

This is a multicenter prospective study of low-risk women who will be recruited if they are having an ultrasound at 36 weeks EGA or greater or if they are presenting to Labor and Delivery for induction of labor. As part of the study, women will have umbilical and middle cerebral artery Doppler studies and the CPR will be calculated by dividing the MCA PI by the UA/PI. Providers caring for study subjects will be blinded to this result. Pregnancy outcomes in women with CPR values less than the 10th percentile for gestational age will be compared to those with CPR values above the 10th percentile.

A secondary aim to our study is to analyze CPR as a continuous variable.

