6.3.2 ENROLLMENT/BASELINE

When the study subject has her ultrasound, the fetus must not be growth restricted as defined by a composite EFW of less than the 10th percentile to continue participation in the study.

The ultrasound assessment of Doppler studies must be complete. If the sonographer cannot obtain satisfactory measurements of both vessels, this information will be recorded but additional subjects will need to be recruited to meet sample size requirements.

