9 STATISTICAL CONSIDERATIONS

9.1 STATISTICAL AND ANALYTICAL PLANS

Statistical analysis is expected to be straight forward in this study. Chi-square or the Fisher exact test will be used to compare binary outcomes. Continuous variables will be compared with the Student *t* test or Mann-Whitney test as appropriate.

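### The crude CPR comparison of undetected SGA cannot show whether CPR adds to the EFW in hand; an EFW-adjusted model should stand beside it

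*Protocol*

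**What the plan says.** - **Entry.** Under Protocol 6.3.2, to continue in the study "the fetus must not be growth restricted as defined by a composite EFW of less than the 10th percentile".
- **Outcome.** Section 4.2.2 lists "Cases of SGA undetected prenatally"; the summary table at the front of the protocol has "Unidentified small for gestational age births". Neither place gives a birthweight cut-off or reference.
- **Comparison.** Section 4.1 forms two groups by CPR: outcomes in women below the 10th percentile for gestational age "will be compared to those with CPR values above the 10th percentile". It also mentions CPR as a continuous variable, without naming a model.
- **Test.** Section 9.1: "Chi-square or the Fisher exact test will be used to compare binary outcomes". No covariate is named.
- **Related items.** Section 4.2.2 also lists "Birthweight/ birthweight percentile" and "Distribution of CPR by EFW". Neither is described as an adjustment.
- **Rationale.** Section 2.1 presents CPR as a way to reach fetuses "who haven't reached their full growth potential but do not appear to be growth restricted".

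**The concern.** Entry and outcome lie on the same weight-percentile scale. Once fetuses below the EFW cut-off have left, every SGA birth among those remaining was missed by the entry scan. The outcome is therefore SGA at birth given an EFW at or above the cut-off. A fetus that entered just above the line is much more likely to become a case than one that entered at the median, and the named test ignores this.

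If low-CPR fetuses tend to have lower EFWs, they will show more undetected SGA for that reason. The rationale in 2.1 concerns fetuses that do not look restricted, so a reader will want to know whether CPR reveals something the EFW did not. A positive crude result cannot separate that from low CPR marking a borderline EFW. The study could then be read as showing that CPR finds missed SGA when the EFW already carried that information.

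**Working it through.** **1. The plan's own figure.** The protocol gives no figure for SGA. Its only sizing figure is 288 low-CPR women for cesarean (9.5: 20% v 10%, 90% power, α = 0.05). With equal groups and a two-sided test:

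n = [1.960·√(2·0.15·0.85) + 1.282·√(0.20·0.80 + 0.10·0.90)]² / 0.10² = (0.990 + 0.641)² / 0.01 ≈ 266.

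The continuity correction gives (266/4)·[1 + √(1 + 4/(266·0.10))]² ≈ 286, close to 288. Nothing in this point touches that calculation.

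**2. Inputs for the SGA outcome.**
- From the protocol: entry at EFW ≥10th percentile (6.3.2); about 300 low-CPR women of 3,000 (5.3), so 300 v 2,700; unadjusted chi-square (9.1).
- Assumed, because the protocol gives no values: SGA means birthweight below the 10th percentile; birthweight SD 12.5% of the mean; EFW error SD 8-10% unless another range is shown; no true change in percentile between scan and birth; CPR-EFW correlation r from 0 to 0.3.
- Two chart readings are shown. In one, the EFW chart is calibrated to the EFW distribution. In the other, EFW is read on the birthweight chart, which excludes more fetuses because EFW is more spread out than birthweight.

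**3. Risk of SGA by starting EFW (calibrated chart).** The correlation of EFW and birthweight z-scores is ρ = 12.5/√(12.5² + e²): 0.842 at e = 8 and 0.781 at e = 10. For EFW z-score x,

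P(SGA | x) = Φ[(−1.282 − ρx)/√(1 − ρ²)].

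| EFW percentile | x | e = 8% | e = 10% |
|---|---|---|---|
| 10th | −1.282 | Φ(−0.375) = 35% | Φ(−0.45) = 33% |
| 20th | −0.842 | Φ(−1.06) = 14% | Φ(−1.00) = 16% |
| 50th | 0 | Φ(−2.38) = 0.9% | Φ(−2.05) = 2.0% |

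By simulation with error 7-10%, the average risk in the 10th-20th band is about 23% (15-17% on the birthweight chart), against under 0.5% above the 50th. That band holds about 50-66% of cases. Cases arise in 3.9-5.1% of enrolled women on the calibrated chart and in 2.9-3.6% on the birthweight chart. Of 3,000 women that is 117-153 and 87-108.

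**4. Crude CPR comparison when CPR adds nothing to EFW.** Set CPR z = r·(EFW z) + √(1 − r²)·(independent noise), and call the lowest 10% of those enrolled low CPR.

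| r | Crude relative risk | Crude chi-square significant at 5% |
|---|---|---|
| 0 | 0.99-1.02 | about 5% |
| 0.1 | 1.16-1.23 | 10-13% |
| 0.2 | 1.34-1.50 | 22-35% |
| 0.3 | 1.56-1.81 | 43-65% |

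Relative risks for r of 0.1 and above are for error 7-10%, significance rates for 8-10%. Repeat runs move the rates by a point or two. Much of the width comes from the chart: at 8% error and r = 0.2 / 0.3 the rates are about 35% / 62% on the calibrated chart and 25% / 45% on the birthweight chart.

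**5. With EFW in the model.** When CPR adds nothing, logistic regression on CPR group and EFW is significant in about 4-6% of studies (calibrated chart), and stratifying finely on EFW gives odds ratios of 0.97-1.00. When CPR does carry birthweight information beyond EFW (8% error, birthweight SD 12%, CPR-birthweight correlation 0.1 / 0.2 / 0.3), the EFW-stratified odds ratios are 1.24 / 1.52 / 1.81, against crude values of 1.42 / 1.95 / 2.65. Adjustment separates the two situations; the crude test does not.

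**The case against.** - **The stated question is prediction.** Sections 2.2 and 3 ask whether CPR predicts adverse outcomes in normally grown fetuses, and no section claims value beyond a continuous EFW. By the protocol's own definition a fetus at the 12th EFW percentile is not restricted, so the crude comparison answers the question asked. This stands.
- **The rates in the table are not false positives of the crude test.** Whenever r is above zero, CPR and SGA really are associated, and rejecting the crude null is correct. The excess exists only against the different null that CPR adds nothing to EFW. This stands and limits the point to interpretation.
- **EFW error alone does no harm to the comparison.** A reader might infer that measurement error around the cut-off is enough to produce a CPR difference. It is not: error makes cases, but at r = 0 the crude test keeps its 5%. A CPR-EFW correlation is also needed. The protocol gives none, though it lists the distribution of CPR by EFW as an outcome, and that would reveal one.
- **The cases are real.** They are small babies at birth, and true slowing of growth over up to 6 weeks also produces them.
- **Adjustment may remove real signal.** If placental insufficiency lowers both EFW and CPR, conditioning on EFW takes out the shared part. This is a reason to report both analyses, not to replace the crude one.
- **An SAP may already add the covariate.** It may. Section 9.1 nevertheless names an unadjusted test and nothing else for this outcome.

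**Conclusion.** The point holds as an inexpensive improvement to one secondary outcome. The crude test is valid for association. If CPR and EFW are correlated, it is uninformative about what CPR adds to the EFW. How often a crude result would be significant with no added value ranges from about 5% of studies at correlation 0 to 43-65% at 0.3, and it rests entirely on the assumed cut-off, birthweight SD, EFW error, chart and correlation.

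The documents do not support two stronger readings: that the SGA comparison is invalid, and that EFW error by itself biases it. The primary cesarean comparison and its sample size are not affected.

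**What to change.** In 9.1 (or the SAP), for SGA at birth:

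1. Keep the crude comparison of CPR groups.
2. Add beside it a logistic model with CPR group and the EFW percentile at the study scan as a continuous covariate.
3. Carry the EFW onto the study form as a number. It is already needed for eligibility and for the CPR-by-EFW outcome, but the schedule of events in 6.3.7 has no line for it.
4. State that any claim of CPR value beyond EFW rests on the adjusted result only.

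Do not try to solve this by requiring a minimum fall, such as 20 percentile points, from EFW to birthweight. A fetus entering at the 15th percentile can fall at most 15 points, so the rule would exclude everyone below the 20th, the band that holds half or more of the cases in the working.

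The cost is a few sentences and one data field, with no new procedure and no extra participants. The downside is that the adjusted association will probably be weaker than the crude one.

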5 STUDY ENROLLMENT AND WITHDRAWAL

5.1 PARTICIPANT INCLUSION CRITERIA

Pregnant women between the ages of 18 and 45 years with low risk pregnancies who present for obstetrical ultrasound at 36 weeks of gestation or later.

5.2 PARTICIPANT EXCLUSION CRITERIA

- Multifetal pregnancy at the time of presentation

- Known fetal chromosomal anomaly
- Known fetal malformation
- Preeclampsia
- Fetal growth restriction
- Prior cesarean section
- Placental abnormalities such as previa or accreta
- Pregestational diabetes

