2.2 RATIONALE

A major contributor to the increasing cesarean rate in the United States is abnormal fetal heart rate tracings leading to concerns for intrapartum hypoxia. Measuring the CPR close or at term may predict which fetuses are at greatest risk for fetal distress in labor and lead to better strategies to reduce the number of cesarean in this group. We aim to study whether an abnormal CPR in low risk women with normally grown fetuses predicts the need for cesarean and other adverse outcomes

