4.2.1 PRIMARY ENDPOINT

The primary endpoint is the cesarean delivery.

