5.3 STRATEGIES FOR RECRUITMENT AND RETENTION

Pregnant women presenting to an obstetrical ultrasound unit or those women on labor and delivery who are not in active labor at or beyond 36 weeks EGA will be approached for enrollment in the study. Women from all ethnic backgrounds will be approached to participate. The actual percentage of minority patients will not be known until patient recruitment is completed. It is expected that there the study population will include adequate representation from a large variety of ethnic groups.

Study subjects are only being asked to undergo two additional measurements during ultrasound after they consent to the study, and we anticipate that this additional work will take no more than 5 minutes of the subject's time. Subjects will not be compensated for participating in the study.

Target sample size is for 3,000 women to enroll, which will give approximately 300 women with CPR < 10th percentile for gestational age.

Accrual rate will depend upon the number of sites participating in the research. There are currently 36,000 deliveries annually within the consortium.

No advertisements to potential study subjects are planned.

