9.5 SAMPLE SIZE

To determine sample size we assumed a 20% cesarean rate for those women who have a CPR <10th percentile and a 10% cesarean rate in women with a CPR ≥10th percentile. With 90% power to detect a difference and $\alpha = 0.05$, 288 subjects with a CPR <10th percentile will need to be enrolled into the study. This means approximately 3,000 subjects will need to be screened.

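### No eligibility criterion removes women whose cesarean is already planned at the Doppler for reasons other than prior cesarean or placental abnormality; if the primary endpoint is any cesarean, they dilute and may bias the CPR comparison

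*Protocol*

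**What the plan says.** **Question.** Protocol 2.2 proposes that CPR near term "may predict which fetuses are at greatest risk for fetal distress in labor". The same section also asks whether an abnormal CPR predicts the need for cesarean.

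**Eligibility.** Section 5.1 asks for a low-risk pregnancy and does not define it. Section 5.2 excludes "Prior cesarean section" and placental abnormalities such as previa or accreta. Section 6.1.1 makes the Doppler conditional on a normal clinical scan, also undefined. Section 6.3.2 sets a lower limit on estimated fetal weight (EFW) and no upper one. Nothing mentions presentation, a scheduled cesarean or a plan for vaginal birth.

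**Recruitment on the labor unit.** Section 4.1 describes women presenting for induction. Section 5.3 describes "those women on labor and delivery who are not in active labor at or beyond 36 weeks EGA", which is wider.

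**Endpoint.** Section 4.2.1 states: "The primary endpoint is the cesarean delivery". The synopsis instead names cesarean for non-reassuring fetal heart tracings as primary. Both the synopsis and 4.2.2 list total cesarean as secondary.

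**Analysis and size.** Section 9.1 plans an unadjusted chi-square or Fisher test. In 9.5, "we assumed a 20% cesarean rate for those women who have a CPR <10th percentile" is set against "a 10% cesarean rate in women with a CPR ≥10th percentile".

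**The concern.** A cesarean decided before the Doppler cannot result from what happens in labor. By removing prior cesarean and placental abnormality, the protocol takes out two common reasons for such a decision and leaves the others to each site's reading of low risk and normal scan.

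Under 4.2.1 each remaining case is a primary event. If these cases are equally common in both CPR groups, they add the same background to both and pull the relative risk toward 1. If they are not equally common, an unadjusted test mixes the difference in planned cesareans with any effect of CPR, and a larger sample does not remove that bias.

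The analysis plan may not be able to repair this later. The schedule of events (6.3.7) does not list planned mode of birth at enrollment, and the chart abstraction in 6.1.1 covers mode of delivery and diagnoses but not the plan at the Doppler. Restricting afterwards to women who labored would condition on events that follow the Doppler.

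**Working it through.** **Inputs from the protocol.** 20% v 10%, 90% power, alpha 0.05 and 288 women with low CPR (9.5); 3,000 enrolled, about 300 with low CPR (5.3), hence 300 v 2,700.

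**Assumption.** The share q of women with a cesarean already planned. The protocol gives none, so 2% to 10% is shown.

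**Step 1: the plan's own figure.** The two-sided, equal-group, pooled-variance formula gives 266 per group. With the continuity correction it gives 286, close to the stated 288. Power for 20% v 10% is 92.1% at 288 v 288 and 99.6% at 300 v 2,700. The actual design therefore has much reserve.

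**Step 2: any cesarean as endpoint, equal shares.** Take 20% and 10% as the rates among the other women. Rate = q + (1 − q) × p. For q = 5%: 0.05 + 0.95 × 0.20 = 0.240 and 0.05 + 0.95 × 0.10 = 0.145.

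| q in both groups | Low CPR | Normal CPR | RR | Power, 300 v 2,700 |
|---|---|---|---|---|
| 0% | 20.0% | 10.0% | 2.00 | 99.6% |
| 2% | 21.6% | 11.8% | 1.83 | 99.1% |
| 5% | 24.0% | 14.5% | 1.66 | 97.9% |
| 10% | 28.0% | 19.0% | 1.47 | 94.2% |

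At q = 5%, planned cases are 0.05/0.145 = 34% of events in the normal-CPR group and 0.05/0.240 = 21% in the low-CPR group.

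**Step 3: any cesarean, unequal shares, no true effect.** The other women have 10% in both groups. The test is a two-sided z test with pooled variance under the null, 300 v 2,700, nominal level 5%.

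| q low v normal CPR | Rates | RR | Rejection |
|---|---|---|---|
| 5% v 3% | 14.5% v 12.7% | 1.14 | 15.5% |
| 3% v 5% | 12.7% v 14.5% | 0.88 | 12.3% |
| 6% v 2% | 15.4% v 11.8% | 1.31 | 44.6% |
| 2% v 6% | 11.8% v 15.4% | 0.77 | 36.9% |

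**Step 4: any cesarean, unequal shares, true 20% v 10%.**

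- q 2% v 5%: 21.6% v 14.5%, RR 1.49, power 87%.
- q 2% v 8%: 21.6% v 17.2%, RR 1.26, power 48%.
- q 5% v 2%: 24.0% v 11.8%, RR 2.03, power 99.9%.

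**Step 5: cesarean for non-reassuring tracings (synopsis).** A planned cesarean is now a non-event, so rate = (1 − q) × p, with 20% and 10% as illustrative rates. Equal shares leave RR at 2.00. The difference shrinks from 10 points to 9.8, 9.5 and 9.0 at q = 2%, 5% and 10%, and power stays at 99.1% or more. With q 2% v 5% the rates are 19.6% v 9.5%, RR 2.06, power 99.7%.

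**Step 6: if 20% and 10% already include planned cases.** Observed rates and power are then those of Step 1. At q = 5% the rates among the other women would be (0.20 − 0.05)/0.95 = 15.8% and (0.10 − 0.05)/0.95 = 5.3%, RR 3.00. The observed 2.00 understates the association in women who plan to labor, but the planned power is intact.

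**The case against.** The strongest reply has five parts.

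1. **The synopsis endpoint largely removes the problem.** This stands. Listing total cesarean as secondary suggests that the fetal-indication endpoint may have been meant, and Step 5 shows a small effect under it. The dilution in Steps 2 to 4 depends on 4.2.1.

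2. **Section 9.5 does not say that its rates apply to women in labor.** This stands. Read plainly, they are rates in enrolled women, and adding q on top may count planned cases twice. A reader might infer that the study is underpowered; the protocol does not support that.

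3. **No passage shows that planned cesarean differs by CPR group.** This stands. "Distribution of CPR by EFW" in 4.2.2 names something to be described and is not evidence of an association. A reader might infer that planned cesareans for size cluster in the normal-CPR group and hide a true effect. The direction is unknown, and the opposite imbalance exaggerates the effect or creates one.

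4. **Women admitted for a scheduled cesarean are not clearly eligible.** This stands in part. Section 4.1 limits the labor-unit route to induction, and 5.1 and 6.3.1 speak of women presenting for ultrasound. Section 5.3 is looser, conflicting wording rather than permission. Likewise, low risk and normal scan could be read as screening out malpresentation or a large fetus. But then eligibility depends on each of the 8 sites' reading, which is a reason for an explicit criterion.

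5. **Need for cesarean in general is also an aim of 2.2.** True, so restricting to planned labor is partly a choice of target population. A cesarean already decided is still not something CPR could predict.

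**Conclusion.** The point holds as a gap in eligibility whose weight depends on an endpoint conflict that must be settled first.

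- **Any cesarean as endpoint:** the relative risk is diluted from 2.00 to between 1.83 and 1.47 for equal assumed shares of 2% to 10%, with power above 94%. With unequal shares the unadjusted comparison is biased in either direction; the illustrations with no true effect reject in 12% to 45% of studies against a nominal 5%.
- **Cesarean for non-reassuring tracings as endpoint:** these women only enlarge the denominator, and the effect is small.

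All shares are assumptions. Power drops below 90% in these examples only with an assumed imbalance in one direction, and not at all if 9.5 already counts planned cases. The harm is to what the result means and to possible bias, not mainly to power. The change is worth making because it is cheap and because the plan at the Doppler is not listed for collection.

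**What to change.** 1. State one primary endpoint by reconciling the synopsis with 4.2.1, and say in 9.5 whether the 20% and 10% include planned cesareans.
2. Add to 5.2: *cesarean already planned at the time of the study Doppler for any reason*.
3. Align the labor-unit wording in 5.3 with 4.1.
4. Add planned mode of birth to the enrollment items in 6.3.7.
5. Define the primary comparison in women planning vaginal birth at the Doppler, and keep cesareans decided later in the analysis. Restricting on the plan at enrollment avoids conditioning on what follows.

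**Cost.** One exclusion line, one recorded item, a few percent fewer eligible women, and a conclusion limited to women planning labor. If the exclusion were applied only after enrollment, 288 low-CPR women would need 288/0.10/(1 − q) enrolled: 2,939, 3,032 or 3,200 at q = 2%, 5% or 10%. Keeping 3,000 leaves 294, 285 or 270 low-CPR women, with power of 99.5%, 99.4% or 99.2% for 20% v 10% at a 1:9 ratio.
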